9.1.1.6 Clinic Visit 4: Day 57 (-3/+7 days)

- Review and record any newly reported safety data including unsolicited AEs or other AEs (e.g., medically-attended AEs, SAEs).
- Record concomitant medications and vaccinations according to instructions in Section 7.6.
- Perform a symptom-directed physical examination (at the discretion of the Investigator; see Section 9.3.6).
- Measure vital signs (body temperature, pulse, blood pressure, see Section 9.3.6).
- Collect a blood sample for immunogenicity assessment (see Table 1) for binding antibody testing to RBD of S protein of SARS-CoV-2 (~6 mL blood) and SARS-CoV-2 viral neutralizing activity (~6 mL blood). (No testing of binding antibody to N protein of SARS-CoV-2 will be performed at this time point).
- Instructions for the subject:
 - Inform the subject that reporting of unsolicited AEs is complete.
 - Remind the subject to call the site immediately to report the following:
 - o If he/she experiences any concerning medical event.
 - Any medically-attended visits that are not routine visits for physical examination or vaccination, such as visits for hospitalization, an emergency room visit, or an otherwise unscheduled visit to or from medical personnel (medical doctor) for any reason.
 - Experience a serious medical event, have a change in overall health or be diagnosed with a new medical condition by a doctor. These should be reported regardless of the perceived relationship between the event and the trial vaccine.
 - Remind the subject to contact the site immediately if he/she has any of the symptoms suggestive of COVID-19. In addition, subjects will be messaged up to twice a week to provide a yes or no response to having COVID-19 symptoms. Those who respond "yes" will be contacted by trial staff for follow-up information if the Investigator considers the symptoms could potentially indicate a COVID-19 case (see Section 9.2.1 and Section 9.5).
 - The subject should also be reminded to contact the site immediately if he/she had a positive SARS-CoV-2 test performed outside of the site, whether they were symptomatic (COVID-19 illness) or asymptomatic at the time of the test.
- Complete the source documents and eCRF for this visit.

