10.5 AEs

An AE is any untoward medical occurrence in a subject which does not necessarily have to have a causal relationship with the investigational product. In this trial, confirmed non-fatal cases of COVID-19 and complications/sequelae are not considered as AEs as they are captured on the CRF pages for COVID-19 illness which are expected outcomes of the trial and are analyzed as efficacy endpoints. Only for any complications and sequelae of COVID-19 illness not mentioned on the COVID-19 summary form in the electronic Case Report Form (eCRF), an AE form needs to be completed.

In this trial, for Phase 2b subjects, information on solicited local and systemic AEs occurring within 7 days after each CVnCoV vaccination and on unsolicited AEs occurring within 28 days after each CVnCoV vaccination are collected.

For all Phase 2b and Phase 3 subjects, information on medically attended AEs up to 6 months after second CVnCoV vaccination and SAEs, AESIs and AEs leading to vaccine withdrawal or trial discontinuation after the second CVnCoV vaccination to EOT Visit are recorded.

No other AEs require recording in the CRF.

The recording of AEs remains unchanged, irrespective of the subject rolling over to the OL-phase or not.

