10.5.4 Unsolicited AEs

Information on unsolicited AEs occurring on each CVnCoV/placebo vaccination day (i.e. dose 1 and 2) and the following 28 days after each CVnCoV/placebo dose are collected for Phase 2b subjects. Data is recorded in the eDiary by the subject to aid AE reporting. The investigator reviews the eDiary and records information on any AEs on the CRF.

Unsolicited AEs are assigned to first or second CVnCoV/placebo dose based on the (reported or imputed) AE date. Unsolicited AEs occurring before dose 2 are assigned to dose 1. Unsolicited AEs occurring after dose 2, are assigned to dose 2. Unsolicited AEs occurring on the day of dose 2 are assigned to either dose 1 or dose 2 as per the following rules:

- If the AE occurred on the day of dose 2 but before vaccination with dose 2, the AE is assigned to dose 1.
- If the AE occurred on the day of dose 2 but on or after vaccination with dose 2, it is assigned to dose 2.
- If the AE occurred on the day of dose 2 and it cannot be determined whether it occurred before, on or after vaccination with dose 2, it is assigned to dose 2.

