10.5.6 Medically Attended AEs

Up to 6 months after second CVnCoV/placebo vaccination (or up to EOT, whatever is earlier), subjects are asked to confirm if they sought medical attention for an AE. Medically attended AEs are defined as AEs with medically-attended visits that are not routine visits for physical examination or vaccination, such as visits for hospitalization, an emergency room visit, or an otherwise unscheduled visit to or from medical personnel (medical doctor) for any reason. The start of a medically attended AE is defined by its start date, irrespective of the date medical attention was sought. A medically attended AE is considered as occurring up to 6 months after second trial vaccination if

$$\text{Start Date of AE} - (\text{Scheduled date of second vaccination} + 1) \leq 180 \text{ days}.$$

i.e. one month is defined as 30 days and the date of the scheduled second vaccination (Day 29) is used in case a subject only received the first vaccination.

Although the 6 months of medically attended AE recording are not re-started when the subject receives an AV, the subject might have received an AV while still being inside the 6 months window after CVnCoV/placebo administration. Thus the medically attended AEs collected might have been caused by an AV. For details how this is handled in the analyses please see Section 12.7.1.

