12.7.7 Adapting the Safety Analyses to the Requirements of Extensive Unblinding

If not explicitly exempted, all safety analyses described in Sections 12.7.1 – 12.7.6 are performed under the conditions of data censoring (described in Section 10.11).

In order to maximally maintain the previous analysis setup while nevertheless aiming at optimally evaluating the collected data the following approach is introduced regarding safety analyses.

1. The above-mentioned analyses (Sections 12.7.1 – 12.7.6) remain unchanged, regardless of extensive individual or site-level unblinding or subjects rolling-over to the OL phase. All definitions still correctly apply and analyses are conducted as originally planned and described above.
2. Additional outputs are planned to account for the massive loss of data due to censoring.
 - a. These additional outputs are closely following the above mentioned safety analyses.
 - b. As far as possible, endpoint definitions and analysis sets are maintained as described in Sections 12.7.1 – 12.7.6.
 - c. No censoring due to unblinding and/or AV receipt is performed.
 - d. AEs/vital sign values are divided into 4 groups: Placebo-only, CVnCoV-only, CVnCoV-AV, AV-only.

AEs/vital sign values are allocated to treatment groups as follows:

- **Placebo-only:** Only placebo has been administered before AE start date / vital signs date. No CVnCoV and no AV must have been administered until then.
- **CVnCoV-only:** At least one dose of CVnCoV and no AV has been administered before AE start date / vital signs date. Placebo might have been administered as well.
- **CVnCoV-AV:** At least one dose of CVnCoV and at least one dose of AV has been administered before AE start date / vital signs date. Placebo might have been administered as well.
- **AV-only:** At least one dose of AV and no CVnCoV has been administered before AE start date / vital signs date. Placebo might have been administered as well.

Treatments are considered “as received”, not “as randomized”.

The following analyses are repeated as described above. All repeat analyses are based on the SAS.

- Overall summary of unsolicited AEs occurring through EOT Visit
- Unsolicited AEs, SAEs, unsolicited AESIs and AEs with fatal outcome, by SOC and PT occurring through EOT Visit

The analyses in this section substitute the analyses of the OL safety endpoints.

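### SAP 12.7.7 splits unsolicited AEs through EOT by whether an authorised vaccine (AV) came first, but the non-serious AE windows close early and do not reopen at the AV, so post-AV events are under-recorded per time at risk

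*SAP*

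**What the plan says.** SAP 12.7.7 adds uncensored safety outputs in which "AEs/vital sign values are divided into 4 groups: Placebo-only, CVnCoV-only, CVnCoV-AV, AV-only". Each event goes to the state that applied at its start date. The outputs include "Overall summary of unsolicited AEs occurring through EOT Visit", followed by unsolicited AEs, SAEs, unsolicited AESIs and fatal AEs by SOC and PT, also through EOT. Two further sentences set their scope and role: "All repeat analyses are based on the SAS" and "The analyses in this section substitute the analyses of the OL safety endpoints". The overall summary, as set out in SAP 12.7.1.3, has rows for medically-attended AEs.

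Collection is narrower than these titles suggest:

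- **General unsolicited AEs.** SAP 10.5.4 limits them to Phase 2b: "Information on unsolicited AEs occurring on each CVnCoV/placebo vaccination day (i.e. dose 1 and 2) and the following 28 days" after each dose. At Day 57 the protocol tells staff: "Inform the subject that reporting of unsolicited AEs is complete" (9.1.1.6, with the same instruction in 9.1.2.6).
- **Medically-attended AEs.** They are collected in both phases to 6 months after the second dose. SAP 10.5.6 concedes that the clock ignores the AV ("Although the 6 months of medically attended AE recording are not re-started when the subject receives an AV").
- **Everything else.** SAEs, AESIs and AEs leading to discontinuation run to EOT; Protocol Table 6 adds intercurrent conditions. Beyond these classes, SAP 10.5 is explicit: "No other AEs require recording in the CRF". It adds that recording does not change on roll-over to the open-label phase.

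SAP 10.5.7 regards an AV inside the 28-day window as unlikely. So the SAP itself expects nearly all post-AV time to fall after general unsolicited collection has closed.

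**The concern.** When CVnCoV is compared with placebo as randomised, a shrinking collection window does little harm, because both arms shrink on the same schedule. Splitting by AV state removes that balance. A subject's post-AV time always follows the pre-AV time, so state is confounded with how much was being recorded. An event that was never collected cannot be recovered by a better denominator.

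Section 12.7.7 gives no common window, no denominators for the four states, no person-time and no caveat. These are the only planned AE tables split by AV receipt. A reader who sets the CVnCoV-AV column beside CVnCoV-only could take a difference in recording for a difference in tolerability.

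**Working it through.** **Inputs.** Protocol Tables 1 to 3 place the contacts at 29+28, 29+182 and 29+364, which gives Days 57, 211 and 393. The SAP 10.5.6 formula (start date minus scheduled second dose plus one, at most 180 days) gives 29+1+180 = Day 210. I use 211 for the rates; the one-day difference is immaterial. Phase 2b is 4,000/36,500 = 11% of planned enrolment. About 49% of subjects had an AV by 18 November 2021 (Protocol 5.2). AV dates are not given, so the AV day d is an assumption and is varied.

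**Medically-attended AEs, CVnCoV-AV against CVnCoV-only.** Assume that 49% of CVnCoV subjects receive an AV, all on Day d, with equal true rates before and after it and follow-up to Day 393. CVnCoV-only then holds the pre-AV time of recipients and the whole follow-up of subjects who never receive an AV. For d up to 211:

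- share of CVnCoV-AV time inside the window = (211 − d)/(393 − d)
- share of CVnCoV-only time inside the window = (0.49d + 0.51×211)/(0.49d + 0.51×393)
- recorded rate ratio = first share divided by second

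| AV day | CVnCoV-AV | CVnCoV-only | Ratio |
|---|---|---|---|
| 90 | 121/303 = 0.40 | 151.71/244.53 = 0.62 | 0.64 |
| 120 | 91/273 = 0.33 | 166.41/259.23 = 0.64 | 0.52 |
| 150 | 61/243 = 0.25 | 181.11/273.93 = 0.66 | 0.38 |
| 180 | 31/213 = 0.15 | 195.81/288.63 = 0.68 | 0.21 |
| 211 | 0/182 = 0 | 211/303.82 = 0.69 | 0 |

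The 49% is itself uncertain. As the AV share goes from none to all, the CVnCoV-only share goes from 211/393 = 0.54 to 1. The ratio then runs from 0.74 to 0.40 for an AV at Day 90, and from 0.27 to 0.15 at Day 180. It stays below 1 throughout.

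**General unsolicited AEs, Phase 2b.** For an AV after Day 57, none of the post-AV time is in the window. The CVnCoV-only share is 57/244.53 = 23% for an AV at Day 90 and 57/288.63 = 20% at Day 180. Phase 3 never has this window.

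**Percentages, which is what the SAP tabulates.** Here I need more assumptions: a constant true AE hazard of 0.005 per day, 20% to 60% of AEs medically attended, 2% to 10% in classes collected to EOT, an 11%/89% phase mix, 49% with an AV, medically-attended collection to Day 210, and AV recipients as the CVnCoV-AV denominator. The percentage with a recorded AE is 1 − exp(−0.005 × collected days), where each day is weighted by the fraction of AEs then recorded. For an AV at Day 57 at the low end, CVnCoV-AV collects 0.2×(210−57) + 0.02×(393−210) = 34.26 weighted days, or 15.7%.

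| AV day | CVnCoV-only vs CVnCoV-AV, low end | High end |
|---|---|---|
| 57 | 15.1% vs 15.7% | 34.7% vs 42.3% |
| 100 | 17.0% vs 12.0% | 39.6% vs 34.4% |
| 210 | 21.5% vs 1.8% | 49.7% vs 8.7% |

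With no true AV effect, the post-AV percentage can be the higher or the lower one.

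**Classes collected to EOT.** Collection is constant, so the person-time rate ratio is 1.00 for any d. Percentages would still differ because time at risk differs: in the same recipients, (393 − d)/d is 336/57 = 5.9 for an AV at Day 57 and 93/300 = 0.31 at Day 300.

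**The case against.** Four stronger readings are tempting, and the documents do not support them.

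- **The medically-attended ratio is 0.40 for an AV at Day 90 and 0.15 at Day 180.** That compares pre- and post-AV time within AV recipients only. The CVnCoV-only column also holds the full follow-up of subjects who never had an AV. Nor is all pre-AV time inside the window once the AV falls after Day 211: for an AV at Day 300 it is 211/300 = 70%.
- **The post-AV column must show fewer AEs.** SAP 12.7.1 plans counts and percentages, not rates. As shown above, an early AV can reverse the direction.
- **The open-label safety question is left with a biased answer.** The open-label endpoints that 12.7.7 replaces (SAP 9.4.1) are SAEs, AESIs, fatal SAEs and AEs leading to trial discontinuation. All are collected to EOT and escape the narrowing.
- **The SAP has no handling at all.** SAP 10.5.5 to 10.5.7 point to 12.7.1 on the question of which vaccine caused an AE, not on collection windows. Censoring under 10.11 and the uncensored repeats in 12.7.1.4 both exist. Section 12.7.1 also already restricts medically-attended AEs to those starting within 6 months of the second dose.

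It is also fair that the tables are descriptive, that no safety test is planned, and that the censored analyses by vaccine group remain. Protocol 3.1.5 indicates that some ordinary reactogenicity after an AV was recorded, so capture is incomplete rather than nil.

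What remains is narrower. The existing 6-month filter acts on events and leaves the time at risk uncut. The unsolicited-AE rows run to EOT across states with different recording, and nothing in 12.7.7 warns the reader.

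**Conclusion.** The point holds for the non-serious and medically-attended parts of the four-state tables: those AEs are under-recorded per time at risk after the AV relative to before it. The 0.64, 0.21 and 0 ratios illustrate the size for the CVnCoV pair; they are not estimates for this trial. They rest on one common AV day, a 49% AV share, equal true rates and full follow-up. Placebo subjects are withdrawn at site unblinding, so these figures do not carry over to Placebo-only against AV-only. The Day 57 closure matters only for Phase 2b; Phase 3 narrows once, at about Day 210/211.

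The SAE, AESI, fatal-AE and discontinuation-AE results are sound on this count, provided that unequal time at risk is shown. This should be corrected in the SAP, but it does not touch the randomised comparisons.

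**What to change.** In SAP 12.7.7:

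1. Limit the four-state through-EOT comparison to the classes collected to EOT: SAEs, AESIs, fatal AEs and AEs leading to trial discontinuation. Give person-time at risk for each state.
2. Show medically-attended AEs by state only with time at risk cut at 6 months after the second dose, to match the event filter already in 12.7.1. Under the same assumptions, the recorded ratio for an AV before the cut then becomes 1.00.
3. Show other unsolicited AEs by state only within 28 days of a trial dose, in Phase 2b (SAS 2).
4. Keep the remaining recorded post-AV events in listings, with a note on when each class was collected.

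The cost is SAP wording, date filters and a person-time derivation, with no new data. The downside is that fewer non-serious post-AV events appear in the comparative tables. For item 3 the post-AV columns will be close to empty, which reflects what was collected.

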10.3.7 Safety Analysis

Clinical Trial Protocol

CureVac AG

No formal statistical testing of safety data is planned.

The descriptive safety analyses will be performed overall by vaccine group, by age group and vaccine group, and by serostatus and vaccine group.

For the open-label phase, applicable descriptive analyses will also be performed by cohort.

Solicited AEs: The frequencies and percentages of subjects experiencing each solicited local and systemic AE within 7 days after each vaccination will be presented by intensity and overall. For subjects with more than 1 episode of the same AE within 7 days after a vaccination, the maximum intensity will be used for tabulations. Similar tabulations will be performed for solicited systemic AEs by relationship to trial vaccination. Solicited local AEs will be by definition considered as related to the trial vaccine. Time to onset (in days) and duration (in days) will also be summarized for each solicited local and systemic AEs. Summary tables showing the occurrence of at least 1 local or systemic solicited AE within 7 days after each vaccination will also be presented.

Unsolicited AEs: Unsolicited AEs including SAEs and AESIs will be coded using the Medical Dictionary for Regulatory Activities (MedDRA) by System Organ Class (SOC) and Preferred Term (PT).

The frequency and percentage of subjects reporting each unsolicited AE within the 28 days after each vaccination and overall will be tabulated at the SOC and PT levels.

Similar tables will be provided for: related unsolicited AEs, Grade 3 or higher unsolicited AEs, medically-attended AEs that occur within 6 months after the second trial vaccination, SAEs, related SAEs, AESIs, related AESIs, AEs leading to withdrawal or trial discontinuation, and SAEs resulting in death through 1 year after the second trial vaccination.

When an AE occurs more than once for a subject within the 28 days post 1 vaccination, the maximal severity and strongest relationship to the vaccine group will be counted.

Only AE post first vaccination will be considered in the summary tables. AE starting prior to the first vaccination will be recorded as medical history.

Data listings of fatal and SAEs will be provided by subject.

Vital signs will be summarized by descriptive statistics at each visit, including change from baseline, and a listing will be provided.

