
On Days 1, 29, 43, 120, and 211 in PBMCs from up to 200 subjects at selected site(s):
 
 • The frequency and functionality of SARS-CoV-2 RBD of S-specific T-cell response after antigen stimulation by ICS to investigate Th1 response and expression of Th2 markers. • The proportion of subjects with a detectable increase in SARS-CoV-2 RBD of S-specific T-cell response. 
Thereby, testing of samples collected on Day 120 and Day 211 is done only in subjects categorized as T-cell responders on Day 29 and/or Day 43. First testing of samples is performed for a subset of these subjects and might be extended to 200 subjects if T-cell response is detectable.
	
In subjects belonging to the Immunogenicity/Reactogenicity subset and selected to take part of the CMI subset:
 
 • The number and percentage of subjects for whom a SARS CoV-2 RBD of S-specific T-cell response is observed • The number and percentage of subjects with a detectable increase in SARS-CoV-2 RBD of S-specific T-cell response

Table 2: Study Endpoints and Estimands for the Open Label Phase (Scenario A only)

Safety	

 Occurrence, intensity and relationship of SAEs and AESIs collected throughout the trial until the EOT. Occurrence of fatal SAEs throughout the trial until the EOT. Occurrence of AEs leading to trial discontinuation. 	
In subjects who received at least 1 dose of CVnCoV and participate in the open-label phase of the trial:
 
 SAE after the first dose with an AV in the open-label phase until the EOT. AESI after the first dose with an AV in the open-label phase until the EOT. Fatal SAE in the open-label phase through EOT. At least 1 AE leading to trial discontinuation.
Exploratory Efficacy	

 Occurrence of first episodes of symptomatic virologically-confirmed (RT-PCR positive) cases of COVID-19 of any severity as assessed by the Investigator. 	
In naïve subjects from the Open-Label Set (OLS) at any time after the first vaccination:
 $VE = 1 - RR \text{ with exact 95\% CI}$ 
Where RR is the ratio of attack rates of COVID-19 cases per 100 person-month in Cohort A: CVnCoV-AV over Cohort B: CVnCoV only.

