12.0 Statistical Methods

Unless otherwise noted, categorical variables are summarized using counts and percentages. Percentages are presented with one decimal place, except for 100% which is displayed without any decimal places and percentages are not displayed for zero counts. Continuous variables are summarized using the number of observations (n), mean, median, SD, 1st Quartile (Q1), and 3rd Quartile (Q3), minimum and maximum values. Mean, median, Q1 and Q3 are presented to 1 decimal more than original data. SD is presented with 2 decimals more than original data. Minimum and maximum match the decimal points in the original data. The maximum number of decimals is 4, unless otherwise stated.

In general, for the blinded study phase, all data summaries are presented overall and by vaccine group. Summaries are further repeated by age group (18 to 60 years and ≥ 61 years) and vaccine group. Efficacy outputs do not have an overall column presented. Selected outputs are additionally presented using further subsetting of the data. This is specified explicitly in the respective sections. Data summaries for the OL-phase are generally presented by cohort, unless otherwise stated.

If not stated otherwise, p-values from statistical tests are two-sided and CIs are calculated using a 95% confidence level.

The factors used for stratification of randomization are age group and country. The primary and key secondary efficacy analyses are not adjusted for these factors, but the analyses are repeated by age group (18 to 60 years and ≥ 61 years) and by country separately. The sensitivity analyses for the primary endpoint using time to event methodology includes both stratification factors in the statistical model.

No imputation of missing data other than that described in Section 10.3 is performed.

All data collected during this trial is displayed in data listings, unless otherwise specified. Screening failures are excluded from all listings and tables if not otherwise stated. Listings include all relevant assigned/derived variables. If not explicitly stated, listings do not show imputed data, but present data as reported.

All data summaries and tabulations are prepared using SAS® Version 9.4 or higher.

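### SAP 12.7.7 replaces the open-label safety analyses with whole-SAS, through-EOT tables, so the SAP text specifies no safety table for open-label participants, the open-label phase or the cohorts

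*SAP*

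**What the plan says.** The open-label safety objective in Protocol version 4.0 concerns subjects still in the trial after unblinding. Protocol 10.3.7 states: "For the open-label phase, applicable descriptive analyses will also be performed by cohort". The synopsis and Protocol 10.3.1 say the same and leave details to an extended SAP. SAP 12.0 makes it the default: "Data summaries for the OL-phase are generally presented by cohort, unless otherwise stated".

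SAP 9.5, Table 2, sets the open-label safety estimands "In subjects who received at least 1 dose of CVnCoV and participate in the open-label phase of the trial". SAP 9.6.7 treats these participants as identical to the Open-Label Set (OLS). The SAE and AESI estimands count events after a first AV dose within the open-label phase. The estimand for deaths is "Fatal SAE in the open-label phase through EOT". SAP 9.6.8 places each OLS subject, retrospectively, in Cohort A (an AV before EOT) or Cohort B (none).

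SAP 12.7.7 then adds uncensored outputs in which "AEs/vital sign values are divided into 4 groups: Placebo-only, CVnCoV-only, CVnCoV-AV, AV-only". The state depends on what the subject had received before the event's start date. "All repeat analyses are based on the SAS". The outputs are "Overall summary of unsolicited AEs occurring through EOT Visit" and, over the same period, SOC/PT tables of unsolicited AEs, SAEs, AESIs and fatal AEs. The section ends: "The analyses in this section substitute the analyses of the OL safety endpoints".

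**The concern.** SAP 9.4.1 and Table 2 keep the open-label safety endpoints and estimands. The tables that would estimate them are replaced by tables with another population, another window and another grouping. Safety follow-up of CVnCoV recipients after unblinding, with and without an AV, is the stated purpose of the amendment. Yet no table specified in the SAP lets a reader see how many OLS subjects had an SAE, an AESI or a fatal event during the open-label phase, or how those events split by AV status or cohort. SAP 6.2, where departures from the protocol are declared, is silent on the substitution.

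**Working it through.** The plan states no figure on this point, so the check compares definitions and then illustrates the effect.

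**1. Definitions side by side**

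| | Open-label plan | Substitute tables (SAP 12.7.7) |
|---|---|---|
| Population | CVnCoV recipients in the open-label phase, i.e. the OLS, which needs a new consent (Table 2, 9.6.7) | SAS: all randomised and dosed subjects, placebo included (9.6.1) |
| Window | SAE, AESI: after a first AV dose, in the open-label phase. Deaths: in the open-label phase. Discontinuation: no window in Table 2; 9.4.1 limits it to Cohort A after an AV dose in that phase | First dose through EOT |
| Grouping | Cohort A/B, per subject (Protocol 10.3.7, SAP 12.0) | Exposure state at onset, per event |

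**2. Do other tables fill the gap?** SAP 10.11 censors safety data from the day after unblinding, and site-level unblinding dates feed the same rule. Events after that day therefore leave the main safety tables. They return in the uncensored repeats of 12.7.1.4 and 12.7.7, both pooled through EOT, and in listings. The OLS is used for enrolment (12.1), demographics (12.2) and concomitant medication (12.4.2). SAP Table 4 has no open-label row. SAP 12.1 does tabulate withdrawals during the open-label phase, with reasons.

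**3. Effect on counts (hypothetical).** Take five CVnCoV recipients with 10 SAEs, and assume the open-label phase starts on Day 300.

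| Subject | AV day | In OLS | SAE days |
|---|---|---|---|
| S1 | 200 | yes | 150, 250, 350 |
| S2 | 320 | yes | 100, 310, 340 |
| S3 | none | yes | 120, 330 |
| S4 | 180 | no | 190 |
| S5 | none | no | 90 |

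- CVnCoV-AV column: Days 250 and 350 (S1), 340 (S2) and 190 (S4), so 4 SAEs.
- Meeting the Table 2 SAE estimand (OLS, after an AV, Day 300 or later): Days 350 and 340, so 2. Of the other two, one precedes the open-label phase and one is outside the OLS. If Table 2 is read as requiring the AV dose itself to fall in the open-label phase, Day 350 drops out and 1 remains.
- Cohort A (S1, S2) has 3 + 3 = 6 SAEs. Three of them (Days 150, 100, 310) fall in the CVnCoV-only column, so the columns are not the cohorts.

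**4. Size (illustrative).** The open-label phase cannot start before 25-Nov-2021, the date of version 4.0. Take first vaccination on the day of randomisation. Then the Day 393 date = randomisation date + 392 days, and maximum open-label days = Day 393 date − 25-Nov-2021 + 1.

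- 16-Apr-2021: Day 393 is 13-May-2022; 170 days; 170/393 = 43%.
- 01-Feb-2021: Day 393 is 28-Feb-2022; 96 days; 96/393 = 24%.

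Post-AV time had also accrued before version 4.0. By 18-Nov-2021 nearly 80% of trial subjects were unblinded and about 49% had received an AV. Protocol 3.1.5 reports 2,535.1 person-years after an AV in more than 11,200 subjects by September 2021: 2,535.1/11,200 × 12 = at most about 2.7 months per subject. That figure covers all CVnCoV trials, so it is only indicative here.

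**The case against.** Much can be said for the SAP.

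- **Authority.** Protocol 4.2.4 lets the SAP modify open-label endpoints, the default in SAP 12.0 yields where another rule is stated, and the change history records 12.7.7 as new. A reader might infer a breach of protocol; the documents do not support that. However, the SAP left the endpoints in place and replaced their analysis. Section 6.2 even edits the wording of the Cohort A discontinuation endpoint without mentioning the replacement.
- **Window.** SAP 9.4.1 and the endpoint column of Table 2 describe SAEs and AESIs as collected over the whole trial to EOT, which the 12.7.7 tables match. This stands: the SAP words the window two ways. It does not cure the population mismatch.
- **Earlier AVs.** A reader might treat AVs taken before the open-label phase as contamination. Cohort A includes them by definition (Protocol 5.1.3, SAP 9.6.8), and a table limited to onset after site unblinding would miss the weeks following an earlier AV. This stands and shapes the fix.
- **Grouping.** Classifying events by exposure at onset is sounder than retrospective cohorts, which credit pre-AV events to Cohort A. This also stands.
- **Availability.** A reader might infer that open-label safety goes unreported or that discontinuations cannot be found. Neither follows. Post-AV events of OLS subjects are in the CVnCoV-AV column, 12.1 gives open-label withdrawals with reasons, the repeated overall summary probably carries the row for AEs leading to withdrawal (12.7.1.3), and SAE, death, unblinding and AV-date listings are planned. What is missing is a table that isolates these events.
- **Intensity.** The Table 2 SAE and AESI estimands have no intensity split. Intensity belongs to the 9.4.1 endpoint, so its absence from the repeats is no departure from the estimands.
- **Unseen list.** The table list (SAP Appendix 4) is a separate document, so further tables cannot be ruled out. The SAP text should still specify them.

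**Conclusion.** The point holds for the SAP text under Scenario A. The substitute tables differ in population from every open-label safety estimand in Table 2, and in window from those for SAEs, AESIs and deaths. They are not by cohort, and the change is undeclared in 6.2. The consequence is dilution: OLS events are pooled with events from subjects outside the OLS and from before the open-label phase. This is more than untidy wording, because a few tables from data already collected would let the trial answer its own open-label objective. It should be fixed, though it does not affect the primary efficacy result.

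No bias is quantified. A reader might turn the 24% and 43% into a claim that 57% to 76% of the substitute tables' content is misplaced (100 − 43 and 100 − 24). The documents do not support that. Those are shares of one subject's calendar time, not of events, and time in the CVnCoV-AV state starts only at the AV dose. 01-Feb-2021 is assumed, and 16-Apr-2021 is a cut-off from the site AR009 unblinding table (SAP 10.12), which also allows for later randomisation. The conclusion rests on the definitions in step 1 of the working, not on these figures.

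**What to change.** 1. Keep the four-state tables of SAP 12.7.7 as supplementary and delete the substitution sentence.
2. Add descriptive OLS tables: SAEs and AESIs (overall, by relationship, and by intensity as in 9.4.1), fatal SAEs, and AEs leading to trial discontinuation.
3. Split them by AV status at onset. Show Cohort A/B totals, the number of OLS subjects entering each state, and person-time in each.
4. Show events with onset after the site-level unblinding date. Show separately, for OLS subjects, post-AV events before that date, because Cohort A includes earlier AV recipients.
5. Reconcile the window wording in 9.4.1 and Table 2, and list any remaining divergence from the protocol in 6.2.

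The cost is some SAP wording and a few extra tables, using onset, AV and unblinding dates already collected. The drawback is small counts in some cells, which is acceptable because the tables are descriptive.
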